### Sample Size Justification

Based on epidemiological modeling for the targeted study countries, province/states of the various site locations, the annualized incidence of moderate to severe/critical COVID-19 cases meeting the primary endpoints definitions has been predicted to be 1.4% for the October-November timeframe. The estimate incorporates that real-world-evidence data and literature data only detected and reported a fraction of SARS-CoV-2 infections.

Furthermore, it includes that, based on literature and real-world-evidence data, only a fraction of all infections meets the moderate and severe/critical COVID-19 case definition and the fraction varies by age as well (increasing with higher ages). Moreover, projections for the selected study regions indicate that incidences will decline over time. Finally, seroprevalence rates are expected to vary between 5-15%.

For the purpose of sample size evaluation, an incidence assumption of moderate to severe/critical COVID-19 cases meeting the primary endpoints definition of 1.4% during the first 3 months of the study, with a 50% reduction in Month 4, and 62% reduction in the months thereafter is assumed in combination with a seroprevalence rate of 10%.

At the time of protocol planning, the epidemiological situation was uncertain: actual seroprevalence rates, degree of social distancing and use of personal protective equipment during the study, local regulations (eg, potential lockdowns, other vaccines if available) potentially becoming in effect during the course of the study and potential drop-outs from the study could impact the disease incidence rate.

To that end, the maximum sample size of approximately 60,000 participants was selected. This sample size was selected, based on the uncertainty of the epidemiological situation in combination with the ability to provide a high probability (approximately 90%) to reach a time to signal within 8 months of the study for a vaccine with an assumed 60% VE.

Based on an estimated case-hospitalization ratio of 2.5% and estimates obtained from reported real-world-evidence data of 3-10% of all SARS-CoV-2 infections meeting the severe/critical COVID-19 definition, this would provide a reasonable likelihood of observing 5 severe cases in the placebo group within the same time frame (8 months).

At the time of writing protocol Amendment 3, the incidence of moderate to severe COVID-19 seen in the US and reported in other COVID-19 vaccine studies is significantly higher than assumed at the time of protocol planning as described above. Furthermore, based on that incidence and modeling there is a high degree of probability that an efficacy signal meeting the prespecified criteria in this amendment will be reached at, or prior to, the time when approximately 40,000 participants will have been followed for a median of 8 weeks from the time of vaccination. Therefore, the sample size is reduced from 60,000 to approximately 40,000.

The operating characteristics of the study design, statistical methods, study monitoring rules and efficacy evaluations specified in this protocol with the chosen event and sample sizes will be described in a separate modeling and simulation report and will be added to the SAP before the first participant is vaccinated.

No additional participants will be recruited for the open-label phase.

### **9.2.2. Immunogenicity Subset (Double-blind Phase)**

All participants included in the Immunogenicity Subset (N = 400) will be added randomly at each stage of the enrollment. Healthy adults (Subset 1a) will be enrolled in Stage 1a, adults with comorbidities (Subset 1b) in Stage 1b, healthy elderly (Subset 2a) in Stage 2a, and elderly with comorbidities (Subset 2b) in Stage 2b, with approximately 100 participants per group as displayed in [Table 3](#). Although Stage 1b and 2b will also enroll participants without comorbidities, only participants with comorbidities will be included in Immunogenicity Subset 1b and Subset 2b.

A sample size of 400 participants, distributed as described in [Table 3](#), is estimated to be sufficient to allow robust description of immune responses to Ad26.COV2.S vaccine. These numbers are expected to provide a solid understanding of the magnitude and kinetics of the humoral response induced by the Ad26.COV2.S vaccine.

### **9.2.3. Immunogenicity Correlates (Correlates Subset)**

Correlates will be assessed in a subset where immune responses and transcriptome modifications are measured in all vaccine recipients who experience a SARS-CoV-2 event, and in random samples of vaccine recipients who have not been infected, in a 1:5 ratio. The goal of this case control study is to assess correlates of risk of SARS-CoV-2 infection (and potential other secondary endpoints) in the vaccine group by comparing vaccine-induced immune responses and transcriptome modifications associated with COVID-19. Also, placebo participants will be included in this subset (placebo infected, seropositive [based on N protein] non-infected and seronegative non-infected), if feasible.

Correlates will also be investigated via a case-cohort design, including measurement of immunological markers in a random subcohort augmented by infected and symptomatic cases.

Controls will be matched with cases from the same stage (age, comorbidities) and other co-factors as deemed appropriate. These will be detailed in the Correlates SAP.

### **9.2.4. Safety**

#### **9.2.4.1. Safety Subset**

While mild to moderate reactogenicity (local injection site and systemic reactions) are expected, AEs that preclude further vaccine administration (if applicable) are not anticipated.

Unsolicited AEs will be captured for a period of 28 days after double-blind vaccination. Solicited and unsolicited AEs will be captured in the Safety Subset, ie, approximately 6,000 participants

(~3,000 from the active group, ~3,000 from the placebo group; and including at least 2,000 from the older age group [ $\geq 60$  years of age] if feasible).

#### 9.2.4.2. All Participants

Adverse events of special interest (from protocol Amendment 5 onwards) and SAEs will be captured in all participants and throughout the study. MAAEs (including new onset of chronic diseases) will be captured in all participants until 6 months after (double-blind or open-label) vaccination with Ad26.COV2.S, except for MAAEs leading to study discontinuation which are to be reported during the entire study. Based on a sample size of approximately 40,000 participants, and approximately 20,000 in the active vaccination group, for SAEs, the observation of 0 events in the database would be associated with 95% confidence that the true rate is less than 0.015%. **Table 7** shows the probabilities of observing at least 1 event (solicited, unsolicited, or SAE) in 1 of the groups at given true AE rates.

**Table 7: Probability of Observing at Least 1 Adverse Event or Serious Adverse Event at a Given True Adverse Event Rate in the Active Group (With a Total Sample Size of 40,000 Participants)**

True AE Rate	Probability of Observing at Least 1 Adverse Event in the Active Group in N Participants	
	Solicited/Unsolicited AEs N=3,000	SAEs N=20,000
0.01%	26%	86%
0.1%	95%	100%
$\geq 0.5\%$	100%	100%

AE = adverse event; N = number of participants receiving study vaccine (Ad26.COV2.S or placebo); SAE = serious adverse events

As of Amendment 7, a passive follow-up approach is adopted: the investigator will place a phone call at Month 18 and Month 24 to collect information on any protocol-required safety assessment (see Section 8.3.1).

In addition, SAEs, AEs, and MAAEs related to COVID-19 need to be reported together with the concomitant medications related to these events until study end. Any confirmatory COVID-19 laboratory information should be reported in the eCRF. Note that 90% of the participants who receive a booster vaccination will be monitored for safety until 1 year post booster vaccination as mentioned in Section 8.3. The remaining 10% of the participants who receive a booster vaccination will be monitored for safety at least for 6 months.

### 9.3. Populations for Analysis Sets

For purposes of analysis, the following populations are defined:

**Full Analysis Set (FAS):** All randomized participants with a documented study vaccine administration, regardless of the occurrence of protocol deviations and serostatus at enrollment. Analyses of safety will be performed on the FAS. Vaccine efficacy analyses can be repeated using the FAS.

**Safety Subset:** subset of the FAS for the analysis of solicited and unsolicited AEs.

**Per-protocol Efficacy (PP) population:** Participants in the FAS who receive double-blind study vaccine and who are seronegative at the time of double-blind vaccination and who have no other major protocol deviations that were judged to possibly impact the efficacy of the vaccine. Participants who became aware of their study vaccine allocation will cease to be part of the PP population. The PA of VE will be based on the PP population. The PP will be the main analysis population for efficacy analyses.

**Per-protocol Immunogenicity (PPI) population:** All randomized and vaccinated participants, including those who are part of the Immunogenicity Subset and for whom immunogenicity data are available, excluding participants with major protocol deviations expected to impact the immunogenicity outcomes. In addition, for participants who experience a SARS-CoV-2 event (molecularly confirmed), samples taken after the event and samples taken outside protocol windows will not be taken into account in the assessment of the immunogenicity. The PPI population is the primary immunogenicity population. For key tables, sensitivity immunogenicity analyses will also be performed on the FAS, including participants who are part of the Immunogenicity Subset for whom immunogenicity measures are available. Excluded samples might be taken into account as well in the sensitivity analysis. Analyses of vaccine immunogenicity and immune correlates of risk will be based on PPI.

The populations for the open-label cross-over, booster and passive follow-up phase are described in the SAP.

The list of major protocol deviations to be excluded from the efficacy for the double-blind analysis and/or immunogenicity analyses will be specified in the SAP and/or this list will be reported into the protocol deviation dataset of the clinical database before database lock and unblinding.

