## 9.2. Sample Size Determination

### 9.2.1. Efficacy (Total Sample Size)

The study TNE is determined using the following assumptions:

- a VE for molecularly confirmed, moderate to severe/critical SARS-CoV-2 infection of 60%.
- approximately 90% power to reject a null hypothesis of  $H_0: VE \leq 30\%$ .
- type 1 error rate  $\alpha = 2.5\%$  to evaluate VE of the vaccine regimen (employing the sequential probability ratio test [SPRT] to perform a fully sequential design analysis; detailed in Section 9.5.1).
- a randomization ratio of 1:1 for active versus placebo

Events are defined as first occurrence of molecularly confirmed, moderate to severe/critical COVID-19 according to the case definition in Section 8.1.3.1 in the PP population. The two co-primary endpoints will evaluate the events at least 14 days after double-blind vaccination (Day 15) and at least 28 days after double-blind vaccination (Day 29) with study vaccine.

Under the assumptions above, the TNE to compare the active vaccine versus placebo equals 154, based on events in the active vaccination and placebo group, according to the primary endpoints case definition of moderate to severe/critical COVID-19 (Section 8.1.3.1).

If the co-primary hypothesis testing is successful for both co-primary endpoints, secondary objectives will be evaluated against a null hypothesis employing a lower limit  $VE > 0\%$ . The

method to perform hypothesis testing of primary and secondary objectives preserving the FWER will be specified in the SAP. The FWER will be controlled at 2.5%.

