##### **9.5.1. Primary Endpoints Evaluation**

The study is designed to test the co-primary hypotheses of VE in the PP population. For both co-primary endpoints the following hypothesis will be tested:

H0: VE  $\leq 30\%$  versus H1: VE  $> 30\%$  and each hypothesis will be evaluated at a 2.5% one-sided significance level.

The co-primary endpoints will evaluate:

- the first occurrence of molecularly confirmed, moderate to severe/critical COVID-19 according to the case definition in Section 8.1.3.1, with onset at least 14 days after double-blind vaccination (Day 15) with Ad26.COV2.S versus placebo, in the PP population, including all events from both age groups, with and without comorbidities.
- the first occurrence of molecularly confirmed, moderate to severe/critical COVID-19 according to the case definition in Section 8.1.3.1, with onset at least 28 days after double-blind vaccination (Day 29) with Ad26.COV2.S versus placebo, in the PP population, including all events from both age groups, with and without comorbidities.

Participants included in the seronegative analysis set are those participants with a negative SARS-CoV-2 serology test result at (double-blind) baseline.

Considering the current COVID-19 pandemic, early detection of VE will be very important. The proposed current analysis setup is designed for continuous sequential analyses (see Section 9.5.1.1), where statistical hypothesis testing is conducted repeatedly on accumulating data, generating an earliest possible signal if and when the splits between the number of events in placebo recipients are much larger compared to the Ad26.COV2.S-vaccinated group for both co-primary endpoints and in such a way that they are unlikely to be due to chance alone using a truncated SPRT. A successful primary efficacy conclusion will require:

1. Establishing the hypothesis H1: VE  $> 30\%$  for each co-primary endpoint

AND

2. A favorable split vaccine:placebo for the subset of primary endpoints meeting the severe/critical COVID-19 case definition (expressed as a VE point estimate against severe/critical COVID-19 molecularly confirmed endpoints  $\geq 50\%$ ) and a minimum of 5 events in the placebo group. This requirement needs to be met for severe/critical events with onset at least 14 days after double-blind vaccination and for severe/critical events with onset at least 28 days after double-blind vaccination.

AND

3. A VE of at least 50% for each co-primary endpoint.

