
Testing done centrally
 
Note: samples for molecular confirmation of SARS CoV 2 infection will be tested if the participant met the prespecified criteria for suspected COVID 19 on COVID 19 Day 1 2 or Day 3 5, as determined locally.
	
Nasal swab for virology testing (molecular confirmation of SARS-CoV-2 infection and viral load testing)
	
At baseline (nasal swab collected by qualified study staff)
 
At Month 6/Unblinding Visit
 
On COVID 19 Day 1 2 (nasal swab collected by the participant at home)
 
On COVID 19 Day 3 5 (nasal swab collected by qualified study staff)
 
Once every 2 days following COVID 19 Day 3 5, until closure of the COVID 19 procedures (nasal sample collected by the participant at home)

	
Serum sample for sero-confirmation of past SARS-CoV-2 infection
	
On Day 1 (pre-vaccination), Day 29, Day 71, Month 6/Unblinding Visit, Year 1/Booster Visit (pre-vaccination, if applicable)
 
At 28 days and 72 days post Year 1/Booster Visit only for participants who received booster vaccination
 
At Month 18 (24 weeks after Year 1/Booster visit)
 
COVID 19 Day 29

	
Nasal swab for virology testing (other respiratory pathogens using a broad respiratory pathogens panel)
	
May be performed on samples collected during a confirmed COVID 19 episode and in a subset of samples from participants with a symptomatic infection.
 
All participants during the open label phase.

	
Saliva samples for virology testing (molecular confirmation of SARS CoV 2 infection and viral load testing)
	
On COVID 19 Day 3 5 (saliva sample collected by the participant at the study site or at home)
 
Once every 2 days following COVID 19 Day 3 5, until closure of the COVID 19 procedures (saliva sample collected by the participant at home)

	
Serum samples for humoral immunogenicity
	
Non-Immunogenicity Subset: on study visits 2 (Day 1; pre-vaccination), 3 (Day 29), 4 (Day 71), 5 (Month 6/Unblinding), 6 (Year 1/Booster; pre-vaccination, if applicable), 8 (Year 1 + 28 days, if applicable), 9 (Year 1 + 72 days, if applicable), 10 (Month 18; 24 weeks after Year 1/Booster), and the early exit visit (if applicable)
 
Immunogenicity Subset: on study visits 2 (Day 1), 3 (Day 29), 4 (Day 71), 5 (Month 6/Unblinding), 6 (Year 1/Booster), 10

Laboratory Assessments	Parameters	Timepoints

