5.1 Inclusion Criteria	Clarifications have been made to the inclusion criterion 4, indicating that for Stages 1a and 2a participants can have a condition that is stable and well controlled except the ones listed in exclusion criterion 15 which are associated with increased risk of progression to severe COVID-19. In addition, medication dose for allowed stable conditions (in all stages of the study) cannot have been increased within 12 weeks prior to vaccination.	Clarification
5.4 Screen Failures	It has been clarified that participants can be rescreened once, also when they meet all in- and exclusion criteria but the 28-day screening period was exceeded.	To allow participants who were found eligible to be enrolled in the study but were not randomized within the 28-day screening window to still participate in the study.
1.1 Synopsis 9.8 Interim Analysis and Committees	Reference to a possible sample size adjustment has been deleted.	Correction; per the VAC31518COV3001 Amendment 1, the sample size of approximately 60,000 participants was selected based

Section Number and Name	Description of Change	Brief Rationale
		on available epidemiology data at the time of Amendment 1 writing.
1.3.1 All Participants	It is clarified that the diagnostic molecular RT-PCR test for SARS-CoV-2 infection (from nasal swab taken at baseline) will be performed at a central laboratory on a retrospective basis. These baseline results are not available in real time, and thus cannot be used to inform participants at time of enrollment.	Clarification
1.1 Synopsis 3 OBJECTIVES AND ENDPOINTS 4.1 Overall Design	It is clarified that molecularly confirmed COVID-19 is defined as a positive SARS-CoV-2 viral RNA result by a central laboratory using a PCR-based or other molecular diagnostic test.	For clarification purposes and to align information included in Section 8.1.3 which states that molecular confirmation of SARS-CoV-2 infection by a central laboratory will be used for the analysis of the case definition.
10.3.10 Source Documents	It has been clarified that source documents for any relevant medical history and prestudy therapies determining eligibility (ie, as specified in the footnotes to the Schedule of Activities) of the participants needs to be collected	To ensure that all necessary information to properly assess SAEs (relatedness) is collected.

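### The per-protocol efficacy population screens for prior infection by baseline serology only, so a seronegative participant who is RT-PCR positive on the baseline swab meets the primary-analysis definition

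*Protocol*

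**What the plan says.** Section 9.3 defines the per-protocol (PP) population as members of the full analysis set who received double-blind vaccine, "who are seronegative at the time of double-blind vaccination and who have no other major protocol deviations" judged able to affect efficacy. It then makes this the primary population: "The PA of VE will be based on the PP population". Section 9.5.1 explains what seronegative means: "Participants included in the seronegative analysis set are those participants with a negative SARS-CoV-2 serology test result at (double-blind) baseline".

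Section 9.2.1 defines the counted event: "Events are defined as first occurrence of molecularly confirmed, moderate to severe/critical COVID-19 according to the case definition in Section 8.1.3.1 in the PP population". Section 9.5.1 sets the two counting windows: "with onset at least 14 days after double-blind vaccination (Day 15) with Ad26.COV2.S versus placebo, in the PP population" and "with onset at least 28 days after double-blind vaccination (Day 29) with Ad26.COV2.S versus placebo, in the PP population".

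Appendix 2 (Section 10.2) lists, under central testing, a nasal swab for molecular confirmation of SARS-CoV-2 and viral load: "At baseline (nasal swab collected by qualified study staff". No subset is named on that line. As background only, the Amendment 2 entry in the amendment history says that this test is run retrospectively: "These baseline results are not available in real time, and thus cannot be used to inform participants at time of enrollment". That limits its use at enrolment but not in defining an analysis set.

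Section 9.3 leaves the list of excluding major deviations to the SAP and/or the deviation dataset.

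**The concern.** Serology detects past infection. It does not detect an infection acquired in the days before vaccination, when antibodies have not yet appeared. RT-PCR does, and the protocol already schedules that test.

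The moderate case definition (Section 8.1.3.1) needs a positive molecular result plus either one listed sign or two listed symptoms, new or worsening. It does not require an earlier negative RT-PCR. A participant carrying virus from before vaccination, still positive on Day 15 or later and then reporting two common symptoms, can satisfy it. Such an event was determined before the vaccine could act. It should fall about equally in both arms and pulls the estimate towards zero.

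Two thresholds are exposed to that pull: rejection of VE of 30% or less, and a VE of at least 50% for each co-primary endpoint (Section 9.5.1).

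The protocol uses molecular information of this kind elsewhere. The asymptomatic-case guideline in Section 8.1.3.4 asks for a positive RT-PCR in someone previously negative. The immunogenicity population in Section 9.3 drops samples taken after a molecularly confirmed event. The primary efficacy population has no equivalent condition.

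**Working it through.** **Inputs from the protocol.** Assumed VE 60%, null VE 30%, one-sided alpha 2.5%, power about 90%, 1:1 allocation, target number of events 154 (Section 9.2.1). Sample size about 40,000 and assumed seroprevalence 10% (Section 9.2.1). Conditional binomial form with π = (1 − VE)/(2 − VE) (Section 9.5.1.1).

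**Step 1: reproduce the plan's figure.** π0 = 0.7/1.7 = 0.4118 and π1 = 0.4/1.4 = 0.2857. The smallest T with one-sided alpha at most 0.025 and power at least 0.90 is T = 154, with critical value 51, alpha 0.0246 and power 0.908. The stated 154 is reproduced.

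**Step 2: add events that the vaccine cannot prevent.** Let a share q of counted events have VE = 0 (π = 0.5) and the rest VE = 60%. Then π = (1 − q) × 0.2857 + q × 0.5, and the estimated VE is 1 − π/(1 − π). The protocol gives no value for q, so these values are assumptions.

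| q | π | Estimated VE | Power at T = 154 |
|---|---|---|---|
| 0 | 0.2857 | 60.0% | 0.908 |
| 1% | 0.2879 | 59.6% | 0.898 |
| 2% | 0.2900 | 59.2% | 0.887 |
| 5% | 0.2964 | 57.9% | 0.849 |
| 10% | 0.3071 | 55.7% | 0.770 |

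Power here is for a single test at 154 events. The sequential boundary is left to the SAP.

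**Step 3: what would have to be true to reach such shares.** Seronegative participants per arm: 40,000 × 0.5 × 0.9 = 18,000. Of 154 true events at VE 60%, placebo has 154/1.4 = 110 and vaccine 44. Let f be the share RT-PCR positive at baseline, and g the share of those later counted as a case. The extra events per arm are x = 18,000 × f × g, and VE = 1 − (44 + x)/(110 + x). For f = 0.5% and g = 5%, x = 4.5 and VE = 1 − 48.5/114.5 = 57.6%. The range, with f and g both assumed:

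| f | g = 1% | g = 5% | g = 20% |
|---|---|---|---|
| 0.2% | 59.8% | 59.0% | 56.3% |
| 0.5% | 59.5% | 57.6% | 51.6% |
| 1% | 59.0% | 55.5% | 45.2% |

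The right-hand column needs one in five baseline positives to be counted as a new case at least two weeks later. The protocol gives no basis for a share of that size.

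**Step 4: the denominator alone.** Removing or keeping the same proportion of non-susceptible people in both arms leaves the rate ratio at 0.4. Suppose instead that people infected in the first 28 days stay in the denominator and cannot have a later event. With 20% infected per year and an early VE of 60%, the placebo loss is 0.20 × 28/365 = 0.01534 and the vaccine loss is 0.4 × 0.01534 = 0.00614. VE is then 1 − 0.4 × (1 − 0.00614)/(1 − 0.01534) = 59.6%. That is the largest shift, about 0.4 points, in the range tried (1.4% to 20% infected per year, early VE 0 to 60%).

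**The case against.** The strongest reply is that the text is silent and has not decided to keep RT-PCR positives. Section 9.3 sends the list of excluding deviations to the SAP, Section 9.5 calls itself a summary, and the part of the protocol reviewed here lacks the eligibility criteria, the objectives and the Schedules of Activities. An at-risk rule may exist there. This stands as a caution: a reader might infer that the sponsor chose to retain such participants, and the protocol does not say so. It does not dispose of the point. The PP definition is stated, it names serology, and being infected at baseline is not clearly a protocol deviation, so the deviation clause does not clearly remove such a participant.

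A reader might also infer that everyone who first tests positive between vaccination and Day 15 or Day 29 contaminates the primary analysis. The protocol does not support this. The onset windows exclude episodes that start earlier, and symptoms must be new or worsening. A known positive opens an episode that normally runs until two consecutive negative swabs and two symptom-free days (Section 8.1.2.2). Severity is the worst in the observation period (Section 8.1.3), and the adjudication committee reviews onset (Section 8.1.3.6). Most later symptoms would therefore belong to the earlier episode. Excluding people on a test taken after vaccination would also condition on a post-randomisation outcome. Swabbing in that period is prompted by symptoms or outside tests, and the prompting symptoms overlap with reactogenicity, so detection may differ by arm.

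Adjudication of onset may also catch some baseline-positive cases one by one. That helps, but it does not define who is at risk.

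**Conclusion.** The point holds for baseline RT-PCR positives only. As Sections 9.3 and 9.5.1 are worded, a seronegative participant with a positive baseline swab belongs to the primary population and can contribute an event that the vaccine could not have prevented.

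The effect is likely small, because several things must coincide: infection before antibodies appear, no episode already open, positivity lasting to Day 15 or later, and new symptoms then. At an assumed 1% to 5% of counted events, VE falls from 60% to between 59.6% and 57.9%, and fixed-size power falls from 0.908 to between about 0.90 and 0.85. The direction is towards lower VE, so an efficacy claim is not inflated. The cost would be some lost power and a slightly low estimate.

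Material dilution of VE is not established, since the protocol gives neither baseline RT-PCR positivity nor the chance that such a participant is later counted. The denominator effect is negligible. This is a worthwhile tidy-up of the definition and does not threaten the trial's conclusions.

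**What to change.** In Sections 9.3 and 9.5.1, define the PP efficacy population as participants who are seronegative at baseline and have no positive central-laboratory RT-PCR on the baseline swab. State how a missing baseline RT-PCR result is handled. Keep the serology-only population as a sensitivity analysis. The target of 154 events does not change.

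The cost is the loss of a few participants and a timing dependency. Because the baseline swab is tested retrospectively and efficacy is monitored at least weekly in the PP population, baseline results must be available before each sequential look as well as before the primary analysis.

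Excluding participants with a positive molecular test between vaccination and Day 15 (or Day 29) should be a supportive analysis only, for the reasons given under the objection.
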